8.1 Treatment Assignment and Randomization

Eligible patients will be randomized in a double-blind fashion to 1 of 3 treatment groups in a ratio of 1:1:1:

- Glepaglutide 20 mg per week, administered as 10 mg SC injections twice weekly
- Glepaglutide 10 mg per week, administered as 10 mg SC injection once weekly and placebo SC injection once weekly
- Placebo, administered as SC injections twice weekly

All 3 treatment arms involve twice-weekly dosing (glepaglutide and/or placebo) to maintain the blind. The first dose is taken on Day 1 and the second dose should be taken on either Day 4 or Day 5 of each treatment week (interval chosen at the randomization visit and adhered to throughout the trial period). Please see [Table 3](#) for a schematic overview.

Table 3: Dosing Regimen

Second Dosing 3 Days after Visit 1								
Day	1	4	8	11	15	18	22	...
Dispensing unit	1		2		3		4	
Twice weekly DB treatment	Vial 1	Vial 2	Vial 1	Vial 2	Vial 1	Vial 2	Vial 1	...
Second Dosing 4 Days after Visit 1								
Day	1	5	8	12	15	19	22	...
Dispensing unit	1		2		3		4	
Twice weekly DB treatment	Vial 1	Vial 2	Vial 1	Vial 2	Vial 1	Vial 2	Vial 1	...

Abbreviations: DB=double-blind

The choice of dosing days will be recorded. Both the patient and Investigator will be blinded to the actual content of each vial (active or placebo); therefore, it is important that the patient selects the correct vial for each administration. Randomization will be performed using a block randomization scheme stratified by patient's weekly PS volume requirements (< 12 L per week versus \geq 12 L/week).

The randomization scheme will be generated prior to the initiation of the trial by an independent statistician/programmer who will not be a member of the trial team; Investigators will not be aware of the block size of the randomization scheme.

Patients will be randomly assigned to trial treatments using an automatic, interactive web response system (IWRS), which is integrated into the electronic data capture system (EDC) and has been validated for the intended use under Title 21 of the US Code of Federal Regulations (CFR) Part 11 (FDA regulation for Electronic Records and Electronic Signatures) and the International Council for Harmonisation (ICH) Guidance E6 for Industry on Good Clinical Practice.

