10.4.1 Visit 1 (Day 1)

During Visit 1, the following assessments will be performed:

- Confirm eligibility based on inclusion/exclusion criteria and that the patient meets the stable PS regimen criteria

- Complete PRO questionnaires (preferably the SBS-I first followed by EQ-5D-5L)
- Record any procedures and changes to concomitant medications
- Perform 12-lead ECG
- Record body weight
- Record vital signs (heart rate, systolic and diastolic blood pressure, and body temperature)
- Record AEs
- Perform short physical examination (driven by SBS symptoms)
- Obtain urine sample for urinalysis
- Obtain blood samples prior to dosing for:
 - hCG pregnancy test (for females of childbearing potential only)
 - Hematology
 - Biochemistry
 - Citrulline
 - PK
 - ADA
 - Bone markers
- Review eDiary information for (if applicable):
 - PS use
 - 48-hour oral fluid intake
 - 48-hour urine volume
 - 48-hour bowel movements/stoma bag emptying
- Record adherence to PS regimen (including weekly schedule, volume, and content) and drinking menu
- Upon approval from Medical Monitor of the stabilization criteria, randomize patient into treatment group using the IWRS criteria set up within EDC
- Administer trial drug and review self-administration procedures, clean-up procedures, and eDiary assignments with patient
- Dispense trial product to patient and discuss treatment compliance with the patient
- Decide on dosing schedule (Day 1 and 4 or Day 1 and 5) (See [Table 3](#))

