12.3.5 Other Efficacy Endpoints

The following **other efficacy endpoints** will be summarized to assess the treatment effect using the FAS. Only descriptive statistics will be presented for these other efficacy endpoints and no inferential statistics will be performed.

Reduction in days on PS ≥ 2 days per week from baseline to Week 24

The number and percent of patients who have a reduction in days on PS ≥ 2 days per week from baseline to Week 24 will be presented for each glepaglutide treatment group and placebo.

Reduction in days on PS \geq 3 days per week from baseline to Week 24

The number and percent of patients who have a reduction in days on PS \geq 3 days per week from baseline to Week 24 will be presented for each glepaglutide treatment group and placebo.

Reduction in duration of PS infusions per week from baseline.

The reduction will be presented descriptively and include the number of non-missing observations, mean, SD, median, minimum, and maximum values.

Concentration trough levels of glepaglutide and metabolites

Concentration trough levels of glepaglutide and metabolites will be summarized descriptively. The number of non-missing observations, mean, SD, median, minimum, and maximum values will be presented by visit.

Change in plasma citrulline levels from baseline to Week 24

The change in plasma citrulline levels from baseline to Week 24 will be presented descriptively and include the number of non-missing observations, mean, SD, median, minimum, and maximum values.

Change in weekly need for parenteral micronutrients (sodium, potassium, magnesium, and calcium) from baseline to Week 24

The change in weekly need for parenteral micronutrients from baseline to Week 24 will be summarized using number of non-missing observations, mean, SD, median, minimum, and maximum values for sodium, potassium, magnesium, and calcium.

Change in PROs (SBS-I and EQ-5D-5L) from baseline to Week 24

The change in patient-reported outcome scores (SBS-I and EQ-5D-5L) from baseline to Week 24 will be presented descriptively and include the number of non-missing observations, mean, SD, median, minimum, and maximum values.

Reduction in bowel movements or stoma bag emptying from baseline to Week 24

The reduction in bowel movements or stoma bag emptying will be presented descriptively by displaying the mean and the 95% confidence interval of the by treatment across the trial period.

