The primary analysis uses a restricted maximum likelihood (REML)–based repeated-measures approach to compare treatment groups with respect to the mean change from baseline in actual weekly PS volume at Week 24. The model will use actual weekly PS volume assessments at Weeks 1, 2, 4, 8, 12, 16, 20, and 24 as an independent variable, and will include the covariates of treatment group, baseline actual weekly PS volume, visit (categorical variable), stratification factor (weekly PS volume requirements <12 L/week versus \geq 12 L/week), and visit-by-treatment group interaction. Variance estimation is based on an unstructured covariance matrix, which does not presume a particular correlation structure for repeated weekly PS volume measurements within patients over time. The primary comparisons are the contrasts (differences in least squares means) between the glepaglutide treatment groups and the placebo group at the Week 24 visit in this mixed-effects model for repeated measures (MMRM).

Missing values will be imputed using multiple imputation methods. For the primary analysis, a Copy Reference (CR) approach is used (main estimator), while for sensitivity analyses, a Jump to Reference (J2R) approach (sensitivity estimator 1) and a Copy Incremental from Reference (CIR) approach (sensitivity estimator 2) will be applied. Details are described in 5.3.1 below.

The Copy Reference approach is justified as the trophic effects on the intestines mediated by glepaglutide would take weeks to abate after treatment withdrawal. A longitudinal growth of the remaining intestines could also have occurred after prolonged therapy, and such modifications would not be expected to fully return to the baseline condition. Other effects of GLP-2 agonism-like reduced fluid secretion from the upper part of the GI tract and effects on reducing motility would, however, be expected to return to the baseline conditions when treatment is withdrawn.

As an additional sensitivity analysis (sensitivity estimator 3), the actual weekly PS volume will be derived using a valid 14-day period prior to the visit. For details on the derivation of actual weekly PS volume within a 14-day period, see Appendix A. This endpoint will be analyzed in the same manner as for the primary analysis for the primary endpoint.

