3.5. OTHER EFFICACY ENDPOINTS

The following other efficacy endpoints will be summarized to assess the treatment effect using the FAS.

The endpoints related to the number of days on actual PS a week will be derived using the selected valid 7-day period used for the primary endpoint. Additionally to summary statistics, these endpoints will be analyzed with the same methodology as for the primary analysis of the confirmatory binary endpoints.

Reduction in days on actual $PS \ge 2$ days per week from baseline to Week 24

The number and percent of patients who have a reduction in days on $PS \ge 2$ days per week from baseline to Week 24 will be presented for each glepaglutide treatment group and placebo

Reduction in days on actual PS \geq 3 days per week from baseline to Week 24

The number and percent of patients who have a decrease in days on $PS \ge 3$ days per weekfrom baseline to Week 24 will be presented for each glepaglutide treatment group and25 August 2022ConfidentialPage 25 of 65

placebo.

Change in duration of actual PS infusions per week from baseline

The change will be presented as descriptive statistics at Weeks 1, 2, 4, 8, 12, 16, 20, and 24.

Concentration trough levels of glepaglutide and metabolites

Concentration trough levels of glepaglutide and metabolites will be summarized descriptively. The number of non-missing observations, mean, SD, median, minimum, and maximum values will be presented by visit.

Change in plasma citrulline levels from baseline to Week 24

The change in plasma citrulline levels from baseline to Week 24 will be presented descriptively and include the number of non-missing observations, mean, SD, median, minimum, and maximum values.

Change in weekly need for parenteral micronutrients (sodium, potassium, magnesium, and calcium) from baseline to Week 24

The change in weekly need for parenteral micronutrients from baseline to Week 24 will be summarized using number of non-missing observations, mean, SD, median, minimum, and maximum values for sodium, potassium, magnesium, and calcium.

For a given visit the parental micronutrients content will be derived from the eDiary values recorded during in valid 7-day period used for deriving the actual weekly PS volume.

Actual PS intake of micronutrients will be used for the analysis involving PS content. Each of the 4 micronutrients will be summarized separately (for sodium, potassium, magnesium, and calcium).

Change in PROs (SBS-I and EQ-5D-5L) from baseline to Week 24

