The change in patient-reported outcome scores (SBS-I and EQ-5D-5L) from baseline to Week 24 will be presented descriptively and include the number of non-missing observations, mean, SD, median, minimum, and maximum values.

For SBS-I, the average ordinal change from baseline to Week 24 for each question will be calculated for all patients combined and by each SBS Anatomical Group (see Section 3.1 for the SBS anatomical subgroups definition). Differences in the average change between each glepaglutide treatment regimen compared to placebo will be tested using a t-test. The sum of scores for each question will be calculated and the difference in change from baseline to Week 24 between each glepaglutide treatment regimen compared to placebo will be assessed using a t-test.

For EQ-5D-5L, results will be presented in three ways.

25 August 2022

- 1. Presenting results from the EQ-5D-5L descriptive system as a health profile at baseline and Week 24: The frequencies and percentages of each level of problem (No problems, Slight problems, Moderate problems, Severe problems, and Extreme problems/unable to do) will be presented at baseline and at Week 24 for each health dimension (Mobility, Self-care, Usual Activities, Pain/Discomfort, and Anxiety/Depression) by treatment group. A further frequency/percentage summary by demographic subgroup (e.g., age group, sex) and/or by SBS Anatomical Group may be presented if applicable.
- Presenting results of the EQ VAS as a measure of overall self-rated health status: The EQ VAS will be presented descriptively for n, mean, standard deviation, median, minimum value, maximum value, 25th percentile, and 75th percentile by treatment group at baseline and at Week 24.
- 3. Presenting results from the EQ-5D-5L index value: The index value will be presented descriptively using n, mean, standard deviation, median, minimum value, maximum value, 25th percentile, and 75th percentile by treatment group at baseline and at Week 24. Differences in the mean values between each glepaglutide treatment regimen compared to placebo will be tested using a t-test. Subgroup tables by demographic and/or baseline characteristics (e.g., age group, sex, smoking status, etc.) and/or by SBS Anatomical Group may be presented if applicable.

Change in bowel movements or stoma bag emptying from baseline to Week 24

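### SAP 3.5 tests SBS-I and EQ-5D-5L by t-tests without baseline score or stratum as covariates and leaves the EQ-5D-5L outcome undefined; ANCOVA on the same data is more precise over a wide range of correlations

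*SAP*

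**What the plan says.** SAP 3.5 heads the endpoint "Change in PROs (SBS-I and EQ-5D-5L) from baseline to Week 24" and opens with a descriptive summary of change. It then adds tests.

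- SBS-I, each item: "Differences in the average change between each glepaglutide treatment regimen compared to placebo will be tested using a t-test".
- SBS-I, sum of scores: "the difference in change from baseline to Week 24 between each glepaglutide treatment regimen compared to placebo will be assessed using a t-test".
- EQ-5D-5L index: item 3 describes the index at baseline and at Week 24, then states "Differences in the mean values between each glepaglutide treatment regimen compared to placebo will be tested using a t-test". EQ VAS and the five-dimension profile are descriptive only.

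No covariate or stratum is named for any of these tests, and SAP 5.1, 5.3 and 5.3.2 add none. By contrast, the primary model in SAP 3.1 includes "covariates of treatment group, baseline actual weekly PS volume, visit (categorical variable), stratification factor". Protocol 8.1 says "Randomization will be performed using a block randomization scheme stratified by" weekly PS volume (below 12 L versus 12 L or more), and protocol 10.4.1 schedules both questionnaires at Visit 1.

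For this class of endpoints protocol 12.3.5 says: "Only descriptive statistics will be presented for these other efficacy endpoints and no inferential statistics will be performed". The list of changes from protocol in SAP section 8 does not mention the PRO tests.

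**The concern.** There are three separate matters.

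First, precision. With about 36 patients per arm, the plan leaves out a prognostic covariate that it already collects. Subtracting baseline, as the SBS-I tests do, forces its coefficient to be 1, which is too much whenever scores regress towards the mean. A test on Week 24 values forces it to be 0. ANCOVA estimates it.

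Second, the EQ-5D-5L index test has no defined outcome. The heading points to change; item 3 points to values at two time points. The two readings have different power and react in opposite directions to a baseline imbalance, so the choice should not remain open at unblinding.

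Third, documentation. SBS-I has 8 items (SAP 5.3.2) plus a sum; with the EQ-5D-5L index that is 10 outcomes, and for two regimens 20 tests, before any anatomical grouping. The protocol excludes inference for these endpoints, and the SAP does not declare the departure.

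**Working it through.** **Inputs.** Patients per arm: 36 (protocol 7.1; protocol 12.7 gives 33-36). The correlation r between baseline and Week 24 score, and the SDs, are not given for either instrument. I assume equal SDs and r = 0.3, 0.5, 0.7, 0.9.

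**The plan's own figure.** The PRO section states none. The only power figures are for the primary endpoint. They reproduce: with differences of 2.2 and 2.0 L/week, SD 2.62, two-sided 0.025 per comparison and a shared placebo arm, t-based power to win on either regimen is 93.4, 95.3, 96.7 and 97.9% at N = 99, 108, 117 and 129, against the stated 93, 95, 96 and 98. Nothing below affects them.

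**Variance of the between-arm difference**, in units of SD² × 2/n:

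- t-test on Week 24 values: 1
- t-test on change: 2(1 − r)
- ANCOVA on baseline: 1 − r²

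So ANCOVA relative to change is (1 − r²)/(2(1 − r)) = (1 + r)/2, and relative to Week 24 values it is 1 − r². The SE reduction is 1 − √ratio.

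| r | ratio vs change | SE smaller by | ratio vs Week 24 | SE smaller by |
|---|---|---|---|---|
| 0.3 | 0.65 | 19% | 0.91 | 5% |
| 0.5 | 0.75 | 13% | 0.75 | 13% |
| 0.7 | 0.85 | 8% | 0.51 | 29% |
| 0.9 | 0.95 | 2.5% | 0.19 | 56% |

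Equal SDs set the size of the gain over change, not its direction. In general Var(change) − Var(ANCOVA) is proportional to (SD at baseline − r × SD at Week 24)², which cannot be negative.

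**Cost of estimating two covariates.** In a simulation of 20,000 null trials per r, with 36 per arm and ANCOVA on baseline plus a stratum that predicts nothing, the ratios were 0.658, 0.755, 0.867, 0.965 against change and 0.927, 0.771, 0.514, 0.193 against Week 24 values. Against change, 36 per arm therefore performs like 36/0.658 = 55, 36/0.755 = 48 or 36/0.867 = 42 per arm at r = 0.3, 0.5, 0.7. With the analytic factor 1 + 2/67 for two covariates, ANCOVA stops winning against change above r = 2/1.030 − 1 = 0.94, and against Week 24 values below r = √(1 − 1/1.030) = 0.17.

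**Type I error** in the same simulation: Week 24 t-test 4.8-5.1%, change t-test 4.9-5.4%, ANCOVA 5.0-5.3%. All three are valid.

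**Chance imbalance.** The baseline difference has SE √(2/36) = 0.236 SD. Given a one-SE imbalance, the change-score estimate moves by (1 − r) × 0.236 = 0.165, 0.118, 0.071, 0.024 SD, against the direction of the imbalance. A Week 24 estimate moves by r × 0.236 = 0.071, 0.118, 0.165, 0.212 SD, with it.

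**What the EQ-5D-5L ambiguity is worth.** For an assumed effect of 0.5 SD at two-sided 0.05 and 36 per arm, using the large-sample variances:

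| r | Week 24 t-test | change t-test | ANCOVA |
|---|---|---|---|
| 0.3 | 56% | 43% | 60% |
| 0.5 | 56% | 56% | 69% |
| 0.7 | 56% | 78% | 84% |

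The two readings agree only at r = 0.5.

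**The case against.** The strongest reply is that nothing here is an error. The t-tests hold their level, the estimates are unbiased over randomisation, the endpoints are outside the gatekeeping, and SAP 5.3.2 calls SBS-I exploratory because it is not validated. That stands, and it is why the point is minor.

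The gain is also conditional on r, which is unknown. At r = 0.9 it is about 2% against change, and it vanishes above about 0.94. With the stratum in the model the SE gain against change at r = 0.7 is 1 − √0.867 = 7%, not 8%. No precision gain is shown for the stratum itself; the reason to include it is consistency with the randomisation and the primary model.

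The 29% and 56% figures need the Week 24 reading, which is the less supported one: the protocol endpoint, the SAP heading and the opening sentence all say change. They describe one branch of an ambiguity, not the expected loss.

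A repeated-measures model is equally defensible for SBS-I, which is collected at every on-site treatment visit. The calculation also does not model integer 0-10 items or missing questionnaires.

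Finally, protocol 12.1 lets the SAP override the protocol, so the added tests are permitted. What is missing is the declaration. That gap is not confined to PROs: SAP 3.5 also adds analysis of the reductions of 2 and 3 or more PS days, and section 8 does not list it.

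None of this gives a reason to prefer the unadjusted tests or to leave the EQ-5D-5L outcome undefined.

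**Conclusion.** The concern holds, at low importance. The plan uses neither baseline score nor stratum as a covariate in the PRO tests, and the EQ-5D-5L index outcome is not specified. Under equal SDs and assumed r of 0.3 to 0.9, baseline-adjusted ANCOVA reduces the SE by 19% to 2.5% against the planned SBS-I change tests; adding a non-prognostic stratum takes back little. If the EQ-5D-5L test is on Week 24 values the reduction is 5% to 56%. The reading of the text is certain; the size depends on a correlation that the documents do not give. The primary and key secondary analyses and the sample size are unaffected.

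**What to change.** In SAP 3.5:

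1. Replace the t-tests with ANCOVA of the Week 24 score (or the change, which gives the same treatment contrast once baseline is in the model) on treatment, the corresponding baseline score and the PS-volume stratum. Report adjusted differences with 95% confidence intervals.
2. State whether the EQ-5D-5L index outcome is the Week 24 value or the change.
3. The text is unclear on whether tests are meant within SBS anatomical groups. If they are, keep small groups descriptive or drop the stratum term there; the minimum of 5 patients per treatment group in SAP 3.1.2, written for the primary endpoint, could be borrowed.
4. Add the PRO inference to the table in SAP section 8 and reconcile it with protocol 12.3.5.

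The cost is a few lines of SAP wording, one table row and trivial programming. No new data are needed.

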3.6. SAFETY ASSESSMENTS

Safety assessments are:

- Adverse events
- Clinical evaluations:
 - Vital signs
 - ECG
- Laboratory assessments:
 - Hematology
 - Biochemistry
 - Urinalysis
 - Standard bone markers
- Immunogenicity assessments

All safety analyses will be conducted using the Safety Analysis Set. No inferential tests of safety data will be performed.

The association between immunogenicity assessments and PK, efficacy, and safety assessments will be summarized as appropriate. See Section 7.7 for immunogenicity analysis details.

Standard bone markers will be assessed as an exploratory endpoint.

See the description of Safety, Section 7 for more details about the analysis for the safety endpoints.

3.7. PHARMACOKINETICS

Blood sample will be collected for pharmacokinetic (PK) evaluation. A total of 9 or 10 samples will be collected from each subject: one sample on visit 1 prior to treatment initiation and one sample on visits 3, 4, 5, 6, 7, 8, 9, and 10 during treatment and one sample at the follow-up visit should the subject not enter the extension trial (see Section 9 – Schedule of Assessments).

Subjects are given scheduled visit days, however, there is an allowed visit window, e.g., visit 3 is ± 2 days and visit 10 is ± 7 days (Section 9). Given these allowed visit windows, the PK sampling times relative to the last drug administration are not pre-determined. Charles River Laboratory will perform the analysis of the PK samples.

When glepaglutide is injected into the subcutaneous compartment, two main metabolites are formed: M1 (ZP1848₁₋₃₅) and M2 (ZP1848₁₋₃₄). The PK samples will be analyzed by use of a liquid chromatography mass spectrometry method optimized for the parent compound, M1 and M2. The method is validated according to regulatory guidelines. Only PK samples from subjects that have been given an active treatment will be analyzed.

25 August 2022

The PK concentrations will be presented as the conceptual concentration (glepaglutide = parent + M1 + M2), the parent compound and the two main metabolites, M1 and M2.

Pharmacokinetic endpoints will be assessed as exploratory endpoints.

